2 RATIONALE

Alphanate® is a high-purity plasma-derived preparation of Factor VIII (Antihemophilic Factor, AHF) in which Factor VIII:C is present in complexes of high-molecular weight multimers of von Willebrand Factor (VWF).

Alphanate® is prepared from plasma found to be nonreactive for hepatitis B surface antigen (HBsAg) and negative for antibodies to human immunodeficiency virus HIV-1 and HIV-2 and hepatitis C virus (HCV) using FDA approved assays. All units of plasma used in the manufacture of

Contains Confidential and Proprietary Information of Grifols Inc.

Alphanate® are also tested for HIV and HCV genomic material using polymerase chain reaction (PCR) assays and using a three-stage sample pooling method approved by the US Food and Drug Administration (FDA). In addition, all units of plasma used in the preparation of Alphanate® have an alanine aminotransferase (ALT) level less than twice the upper limit of normal for the assay method used.

Two specific viral reduction processes are used in the manufacture of Alphanate®:

- (1) treatment with an organic solvent/detergent mixture [tri(n-butyl)phosphate (TNBP)/polysorbate 80] to inactivate lipid-enveloped viruses such as HIV-1, HIV-2, hepatitis B (HBV) and HCV; and
- (2) exposure of the lyophilized product in the final container to heating for 72 hours at 80°C.

These processes have the theoretical potential to expose new antigenic sites in the Factor VIII molecule. If new antigenic entities are created, individuals with hemophilia A who have not developed antibody inhibitors in response to treatment with other plasma-derived Factor VIII concentrates could develop inhibitors to these new antigenic sites. The generation of antibody inhibitors to Factor VIII could result in treatment complications.

3 OBJECTIVE

The objective of this study is to determine the immunologic and overall safety associated with long-term use of Alphanate® in individuals diagnosed with severe hemophilia A (Factor VIII:C less than 0.01 IU/mL), who have been previously treated with plasma-derived Factor VIII products other than Alphanate® and who have no history of developing either antibody inhibitors to Factor VIII or nonspecific inhibitors of coagulation.

4 STUDY DESIGN

This is a phase IV, non-randomized, multicenter study involving at least 50 evaluable subjects diagnosed with severe hemophilia A (levels of Factor VIII:C in plasma less than 0.01 IU/mL), who are male, at least six years of age and not more than 65 years of age, and with a Karnofsky Performance Score of at least 50. All subjects will have adequate immune system function (CD4 count must be greater than or equal to 400 cells/µL and subject must not have an immune system impairment or damage by disease or treatment).

Contains Confidential and Proprietary Information of Grifols Inc.

Enrolled subjects will be treated at home and with in-clinic therapy exclusively with Alphanate[®] as their sole source of FVIII concentrate for prophylaxis and treatment of all bleeding episodes and surgical procedures for a period of at least two years and a minimum of 50 exposure days, or, if 50 exposure days are not reached, for a maximum of 30 months. Alphanate[®] will be administered in accordance with the subject's usual pre-study treatment regimen. An exposure day is defined as any day on which a subject receives one or more infusions of any Factor VIII containing product. However, only one exposure day will be accrued for each surgical episode, regardless of the number of days of treatment or the number of infusions of Factor VIII associated with that surgical procedure.

A subject will continue treatment, as specified above, unless

- The subject develops inhibitors to Factor VIII at a titer greater than or equal to 5 Bethesda units (BU/mL);
- treatment with Factor VIII becomes ineffective at providing hemostasis even for a subject who has developed inhibitors with a titer of less than 5 BU/mL; or
- the subject exhibits severe or serious adverse events that prevent completion of participation in the study.

In all instances, only the inhibitor titer obtained by the central reference laboratory will be used to determine the subject's eligibility to continue his participation in the trial.

The primary endpoint of this study is:

the incidence of Factor VIII inhibitor after exposure to Alphanate[®].

The secondary endpoints are:

1. The frequency, nature, causality and severity of adverse events.
2. The occurrence of changes in biochemical parameters which would indicate alterations in renal or hepatic function.
3. Evidence for seroconversion to HIV-1/HIV-2, HAV, HBV, HCV and parvovirus B19 for subjects who are seronegative for these viruses upon enrollment.
4. The amount of product used per year as part of at-home prophylaxis and therapy for bleeding episodes.

Contains Confidential and Proprietary Information of Grifols Inc.

5. A physician's qualitative assessment of hemostasis (evaluated as "None," "Moderate," "Good," or "Excellent") in response to therapy with Alphanate® received by the subject in a hospital or at another location under the physician's direct supervision.

The design of this study satisfies the recommendations of the European Commission Committee for Proprietary Medicinal Products (CPMP) regarding eligibility criteria and end points for studies, in previously-treated patients, of concentrates with marketing authorization in which a manufacturing process has been added. In addition, this study conforms to the CPMP recommendation that all enrolled subjects be vaccinated against hepatitis A and B. Any candidate for this trial who has not yet been immunized against hepatitis A will be offered a course of hepatitis A vaccination.

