7.12 Treatment with Other Blood Products

Subjects will be treated for hemophilia A exclusively with Alphanate® during the course of the study. If whole blood or other blood products are used during surgery or during the control of hemorrhagic episodes, the exact dose, date and duration of treatment and prescription etiology will be entered in the appropriate case report forms.

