7.14 Discontinuation of Subjects

A subject will be discontinued from the study if any of the following occurs:

Contains Confidential and Proprietary Information of Grifols Inc.

- A severe or serious adverse event, which, based on medical judgment, prevents completion of participation in the study (See Section 10 for classification of adverse events).
- Development of a Factor VIII inhibitor either
 - at a titer at or above 5 BU/mL **or**
 - at a titer lower than 5 BU/mL but that renders Alphanate[®] treatment ineffective in providing hemostasis.
- Treatment of the subject with another Factor VIII concentrate while in the study.
- Treatment of the subject with immunosuppressive drugs.
- Unwillingness and non-compliance of the subject with the provisions of the protocol.
- Withdrawal of the subject from the study on his/her own volition.
- Death of the subject during participation in the study.

If a subject withdraws after treatment, the clinical site will attempt to obtain all possible follow-up safety data from that subject.

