8.1 Primary Endpoint

Incidence of antibody inhibitors to Factor VIII in at least 50 evaluable subjects will be determined following a period of at least two years and a minimum of 50 exposure days or if 50 exposure days are not reached, a maximum of 30 months. Only one exposure-day will be accrued for each surgical episode independent of the number of days of treatment or the number of infusions. For the purpose of this endpoint only, a subject is determined to be evaluable when his clinical experience after the date of enrollment includes at least 50 CEDs of treatment with Alphanate[®] or when he develops inhibitors with a titer greater than or equal to 5 BU/mL as determined by the central reference laboratory.

Contains Confidential and Proprietary Information of Grifols Inc.

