9.3 Additional Analyses

9.3.1 Exposure to Study Drug

Total exposure through the number of Factor VIII units infused will be summarized with descriptive statistics by dosing. Frequencies and percentages will also be used to summarize the number of infusions at each dosing.

Exposure to study drug will be listed for each subject to indicate the complete usage pattern including number of exposures at home and in clinic, reason for infusion, whether hemostasis was achieved (if evaluation available) and physician comments.

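### The SAP derives no exposure days, so no planned summary shows which subjects meet the protocol's 50-CED rule for evaluability on the primary endpoint

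*Protocol*

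**What the plan says.** **Evaluability.** Protocol 8.1 seeks the inhibitor incidence in at least 50 evaluable subjects. For this endpoint a subject is evaluable when "his clinical experience after the date of enrollment includes at least 50 CEDs of treatment with" Alphanate, or when the central laboratory finds an inhibitor of 5 BU/mL or more. Protocol 9.2.1 and SAP section 4 state their decision rule for 50 evaluable subjects followed for two years.

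**Counting rule.** Protocol 8.1 adds: "Only one exposure-day will be accrued for each surgical episode independent of the number of days of treatment or the number of infusions". Section 4 has the same surgical rule.

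**Duration.** Section 4 sets treatment "for a period of at least two years and a minimum of 50 exposure days, or, if 50 exposure days are not reached", up to 30 months. Its own definition reads: "An exposure day is defined as any day on which a subject receives one or more infusions of any Factor VIII containing product".

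**Other products.** Protocol 7.12 requires hemophilia A to be treated only with Alphanate, but also provides for recording "If whole blood or other blood products are used during surgery or during the control of hemorrhagic episodes". Protocol 7.14 lists "Treatment of the subject with another Factor VIII concentrate while in the study" as a reason to discontinue. It does not list other blood products.

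**SAP.** Section 5 defines a Safety Population and nothing else, and 9.1 analyses the primary endpoint on it. Section 7.3 derives baseline and the on-treatment period, but neither exposure days nor CEDs. Section 9.3.1 summarises Factor VIII units and will "summarize the number of infusions at each dosing". It also plans a per-subject usage listing with the number of exposures by place and the reason for each infusion.

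**The concern.** The trial asks whether Alphanate's processing creates new antigenic sites (Protocol section 2). A finding of no inhibitors is informative only to the extent that subjects were exposed to Alphanate, and the protocol's yardstick for enough exposure is 50 CEDs. If the report cannot say how many subjects reached 50, a reader cannot tell a clean result from an under-exposed one, or check whether the required 50 evaluable subjects were obtained.

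The planned exposure summaries look as though they fill this role but do not. Units and infusion counts can be high in a subject with few CEDs, particularly after surgery.

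The two product definitions add a smaller difficulty. The count that governs treatment duration in section 4 and the count that governs evaluability in 8.1 are not the same variable, so a programmer asked to derive exposure days would have two protocol rules to choose from.

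**Working it through.** No figure in the plan depends on the exposure-day count, so there is nothing to reproduce. The check compares the rules and then gauges the size.

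**1. Infusions against CEDs**

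Inputs:
- about two weeks of post-operative treatment (Protocol 7.9.2);
- one CED per surgical episode (sections 4 and 8.1);
- assumed: two surgeries, 20 single-infusion bleed days, and *k* = 1 to 2 infusions per surgical day. Protocol 7.9.2 gives twice daily for serious hemorrhages, not for surgery, so *k* = 2 is an assumption.

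Results:
- infusions = 2 × 14 × *k* + 20 = 48 (*k* = 1) or 76 (*k* = 2);
- calendar days with an infusion = 2 × 14 + 20 = 48;
- CEDs = 2 × 1 + 20 = 22.

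This subject has 22 exposure days under section 4 and under 8.1 alike. The example shows only that infusions, and even infusion dates without the surgical rule, do not give CEDs.

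**2. Ending at 30 months below 50**

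Reaching 50 takes 50 / 24 = 2.08 exposure days per month over two years, or 50 / 30 = 1.67 per month over 30 months. A subject averaging 1.5 per month (assumed) has 1.5 × 30 = 45 at month 30. He has reached the section 4 maximum, is not evaluable under 8.1 unless he has an inhibitor of at least 5 BU/mL, and stays in the Safety Population. No other product is involved.

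**3. Section 4 against 8.1**

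| Type of day | Section 4 | 8.1 |
|---|---|---|
| Alphanate given, with or without another product | 1 | 1 |
| Surgical episode treated with Alphanate | 1 in total | 1 in total |
| Non-surgical day, other Factor VIII containing product, no Alphanate | 1 | 0 |

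Only the last row differs. With 49 Alphanate days and one such day (assumed), section 4 gives 50 and 8.1 gives 49.

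**4. Size for the primary result**

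With no inhibitors among *n* subjects, the exact one-sided 95% upper bound is 1 − 0.05^(1/*n*):
- *n* = 50: 5.8%
- *n* = 49: 5.9%
- *n* = 45: 6.4%

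Reading 0/50 when only 45 subjects are evaluable therefore understates the bound by about 0.6 percentage points. With one inhibitor case the percentages are 1/50 = 2.0% and 1/45 = 2.2%. These bounds are used for scale only. They are not the interval stated in Protocol 9.2.1, which is a separate matter.

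**The case against.** Several points on the other side have force.

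- **The listings may suffice.** SAP 6.6 lists all collected data by subject and date, and the 9.3.1 listing includes the reason for infusion. A reader could count CEDs by hand. This stands, so it would be wrong to say that the SAP cannot detect a shortfall. But no display makes the count, and applying the surgical rule by hand to 50 or more subjects over two years is neither specified nor reproducible.
- **The SAP denominator is unaffected.** All treated subjects are in the Safety Population, so no subject drops out of the planned percentage. This also stands. What is affected is whether the protocol's 50 evaluable subjects can be shown.
- **Fifty is a minimum.** Protocol 9.1 speaks of 50 to 80, so losing one or two evaluable subjects may not matter. That holds only if the number evaluable is known.
- **Stopping at 30 months below 50 is intended.** It is. The concern is that such subjects are not identified.

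On the product wording, a reader might infer that subjects will be released early on non-Alphanate days and so lost as evaluable. The documents do not support that as a general effect. Protocol 7.12 requires exclusive Alphanate treatment and another concentrate leads to discontinuation. A day with both products counts under either rule. Section 4 sets minimums and does not order release when they are met.

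**Conclusion.** The concern holds for the SAP: the protocol defines who is evaluable for the primary endpoint, and the SAP neither derives the variable behind that definition nor reports how many subjects meet it. It should be corrected before the final analysis. It does not invalidate the planned safety tabulation.

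The numerical effect is modest under the assumptions shown: about 0.6 percentage points on a zero-event upper bound if five of 50 subjects fall short. The documents do not say how many will, so the true size is unknown. The main loss is interpretive, since exposure cannot be set beside the inhibitor result.

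The difference between section 4 and 8.1 is a genuine contradiction in the text but probably a rare one in practice. It needs a non-surgical day with another Factor VIII containing blood product and no Alphanate, and it changes a subject's status only if he is at the threshold. The documents give no frequency for such days.

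**What to change.** **SAP.**
- In 7.3, define Alphanate CEDs per subject from dated infusion records: one per calendar day with Alphanate, and one per surgical episode. State how infusions are assigned to an episode.
- In 9.3.1 and Table 12.1, summarise CEDs and report the number and percentage of subjects meeting the 8.1 definition, separating those with 50 CEDs from those qualifying through an inhibitor of at least 5 BU/mL.
- For every inhibitor case, give the CEDs at the first positive titre.

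**Protocol.** Reconcile section 4 with 8.1 so that one on-study exposure-day definition applies. Because section 4 also governs how long subjects are treated, the choice of definition is for the sponsor and investigators.

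**Cost.** One derived variable and slightly more analysis work. The diary already records the date and reason for home infusions (Protocol 7.9.1), the drug utilisation record carries a date used (16.1), and the CRF records dates of other blood products (7.12). This assumes that in-clinic infusions are dated per administration in the database, which should be confirmed.

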5 SELECTION OF SUBJECTS

The following entrance criteria must be satisfied for a patient to be enrolled into this study:

5.1 Inclusion Criteria

1. The subject must be male, at least six years of age and not more than 65 years of age.
2. The subject must have signed and dated an Informed Consent Form and Patient Authorization for Release of Information approved by the appropriate Institutional Review Board (IRB) prior to screening and enrollment. If the subject is a minor (*i.e.*, less than 18 years of age) both he and his parent or legal guardian must sign and date the informed consent.
3. The subject must have been diagnosed with severe hemophilia A and must have levels of Factor VIII less than 0.01 IU/mL.
4. The subject must have received treatment with cryoprecipitate, Factor VIII concentrates, and/or whole blood, for at least 150 cumulative exposure days (CEDs) prior to enrollment.
5. The subject must not have received treatment with cryoprecipitate, Factor VIII concentrate, or any other blood product, for at least 72 hours prior to screening.
6. The subject must never have been diagnosed with inhibitors to Factor VIII at any detectable titer.

Contains Confidential and Proprietary Information of Grifols Inc.

7. The subject must never have been diagnosed with nonspecific inhibitors of coagulation.
8. The subject must test negative for the presence of Factor VIII inhibitors at screening and enrollment.
9. The subject must have CD4 counts greater than or equal to 400 cells/ μ L.
10. The subject must have been vaccinated against hepatitis A and hepatitis B, or have evidence of antibodies against hepatitis A and hepatitis B. However, a subject who has no prior immunity against hepatitis A will be offered a course of vaccination for hepatitis A.
11. The subject must have a Kamofsky Performance Score of at least 50 (Appendix 1).

5.2 Exclusion Criteria

1. The subject is receiving any immunosuppressive medications including intravenous immunoglobulins at the time of enrollment.
2. The subject has clinical signs or symptoms of an infection, such as fever, chills or nausea during screening or enrollment.
3. The subject has a history of frequent reactions to Factor VIII concentrates (e.g., chills or headaches).
4. The subject has received treatment with Alphanate® (Solvent-Detergent/ Heat-Treated).
5. The subject is immunocompromised (including HIV+ status or has an impaired immune system due to disease or treatment).

6. TEST MATERIAL

Alphanate® is prepared from plasma found to be nonreactive for hepatitis B surface antigen (HBsAg) and negative for antibodies of HIV-1/HIV-2 and HCV using FDA approved assays. All units of plasma used in the manufacture of Alphanate® are also tested for HIV and HCV genomic material using polymerase chain reaction (PCR) assays and using a three-stage sample pooling method approved by the US Food and Drug Administration (FDA). In addition, all units of plasma used in the preparation of Alphanate® have an

Contains Confidential and Proprietary Information of Grifols Inc.

alanine aminotransferase (ALT) level less than twice the upper limit of normal for the assay method used.

Alphanate® is manufactured by cryoprecipitation, polyethylene glycol (PEG) precipitation, heparin-agarose chromatography and glycine precipitation. Two specific viral reduction procedures are used in the manufacturing process:

- At an intermediate step in the manufacture of Alphanate®, the product is treated with an organic solvent/detergent mixture [tri(n-butyl)phosphate (TNBP)/polysorbate 80] to inactivate lipid-enveloped viruses such as HIV-1/HIV-2, hepatitis B and C (HBV, HCV); and
- The lyophilized product is heated at 80°C for 72 hours in the final container and meets all internal specifications of Grifols Inc.

However, virus reduction methodologies and testing techniques cannot fully eliminate the risk of viral transmission.

Alphanate® is provided as a lyophilized powder in a vial containing at least 40 International Units Factor VIII:C/mL (200 IU/vial) (IU; all subsequent references to IU will be expressed as units) after reconstitution. A label indicating the manufacturer, lot number, number of Factor VIII:C units, and reconstitution volume is affixed to each vial. A vial containing the appropriate volume of sterile water for injection (SWI), USP, is provided with each vial of Alphanate®.

Alphanate® used in this clinical trial has met all internal product release specifications of Grifols Inc.

7 STUDY PROCEDURES (SEE APPENDIX 2)

7.1 Screening

All of the following procedures and laboratory procedures will be performed: a) **at least 72 hours after the most recent administration of cryoprecipitate, Factor VIII concentrate or any other blood product**, and b) before the first administration of Alphanate®.

See the table in Appendix 2 for the listing of laboratory tests to be performed.

1. Before any invasive screening tests are performed, the subject will be presented with an IRB-approved informed consent form and patient authorization form, which will be explained to him. The subject will not participate in any part of the clinical trial, including the initial screening until he has signed and dated the forms to indicate that he understands and

Contains Confidential and Proprietary Information of Grifols Inc.

agrees to its contents (if he is less than 18 years of age, his parent or legal guardian must agree and sign).

2. The subject's medical and past treatment history will be reviewed to ascertain whether he meets all the entry requirements for the study.
3. Each subject will receive a physical examination that will include: vital signs (pulse, respiratory rate, oral temperature, blood pressure), height, weight, and a description of any physically observable abnormal conditions.
4. Hematologic status will be assessed by: complete blood count (CBC) with white blood cell (WBC) differential and platelet count.
5. Immune system function will be assessed, including a CD4 count.. Any patient with suspicion of a compromised immune system must be approved by the sponsor prior to enrollment.
6. Factor VIII coagulant activity (Factor VIII:C) will be assessed both by the local laboratory and the central reference laboratory **The value obtained by the central reference laboratory will determine the subject's eligibility.**
7. The Factor VIII inhibitor level (BU/mL) will be determined. Two sets of samples will be drawn: one for analysis at the local laboratory of the clinical site, and the other sample for analysis at the central reference laboratory. **The value obtained by the central reference laboratory will determine the subject's eligibility.**
8. Serum chemistry tests will be performed: alanine aminotransferase (ALT), aspartic aminotransferase (AST), alkaline phosphatase (AP), lactic acid dehydrogenase (LDH), blood urea nitrogen (BUN), total bilirubin and creatinine.
9. Viral and serological tests will be conducted: including testing for HBsAg, and for antibodies to HAV, HBcAb, HBsAb, HCV, HIV-1/HIV-2 and parvovirus B19 (by routine immunoassay).
10. A sample of venous blood will be drawn from which approximately 5 mL of serum will be prepared and aliquoted into three vials of at least 1.5 mL of sample each. The samples will be frozen and retained at -20°C in the event that they are required for later serological or virology tests.

Contains Confidential and Proprietary Information of Grifols Inc.

